9.3.3 Covariates

The following baseline characteristics will be available from the GloBE-Reg data and overlap with the baseline characteristics from NordiNET/ANSWER and GeNeSIS:

- Sex
- Country
- Age at initiation of GH treatment (any GH treatment)
- Duration of GH Treatment at study inclusion (GH naïve or non-naïve patients)
- Height
- Weight
- BMI
- IGF-I
- Bone age
- Medical history of neoplasms
- Medical history of T2DM
- Diabetes risk factors: obesity

9.4 Data sources

The data for this study will be drawn from GloBE-Reg. In line with EMA guidelines⁵ (EMA/426390/2021, current version), the GloBE-Reg is an international consortium-led registry project owned by the University of Glasgow, with industry partners (including Novo Nordisk A/S), major professional endocrine societies, and patient representatives, collecting real-world data on the safety and clinical parameters of several medicinal products (including somapacitan) in the field of rare bone and endocrine conditions.

The GloBE-Reg platform was initiated on 1st October 2022. ¹⁷ The registry is designed to collect information on any child or adult who is about to start a certain treatment or where treatment is being/has been considered for a bone or endocrine condition. At the time of finalising this protocol,

^aThis will be reported at shorter intervals if data allows

^bEOS will differ from patient to patient.

^cOnly for those who are expected to reach near adult height during the study.

Protocol		Date:	17 July 2024	Novo Nordisk
Study ID: NN8640-4787	CONFIDENTIAL	Version:	3.0	
UTN: U1111-1294-5941		Status:	Final	
EU PAS No.: Pending		Page:	23 of 48	

GloBE-Reg is active in several countries in Europe, US, Asia and South America. Ethics committee approvals have been obtained in these countries.

The present study will investigate the subset of the paediatric patients with GHD from GloBE-Reg treated with somapactitan. As per the protocol, the planned number of patients to be included in the study is at least 400 (both naïve and non-naïve) male or female patients (below 18 years at the time of enrolment) with confirmed diagnosis of GHD. A minimum set of parameters can be extracted from GloBE-Reg e.g., every 6 months.

Details for neoplasms, T2DM and medication errors should be recorded in GloBE-Reg and will be included in the study data for eligible patients.

9.5 Study sample size

The sample size calculations are performed for the primary endpoint (number of ADRs) and based on previous experience from the NordiNet[®] IOS⁶ where 2% of the paediatric patients with GHD experienced an ADR.

Table 9-4 shows the 95% confidence interval for an incidence of 2%, derived using the Wilson-score method.

Table 9-4 Sample size table (Wilson-score method)

Sample size	95% CI
100	(0.55, 7.00)
200	(0.78, 5.02)
300	(0.92, 4.29)
400	(1.02, 3.89)
500	(1.09, 3.64)

Based on the table above, a sample size of at least 400 patients (inclusive of both naïve and non-naïve paediatric patients) would be required to rule out the doubling of the incidence for ADRs. Therefore, the study is planned for the sample size of 400 patients.

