9.1 Study design

EU PAS No.: Pending

This is a non-interventional, multi-national, single-treatment arm, observational, registry-based study to investigate the long-term safety and clinical parameters of somapacitan in paediatric patients with GHD under routine clinical practice conditions. The study design is shown schematically in Figure 9-1.

Figure 9-1 Schematic diagram of the study design

Abbreviations: GHD = growth hormone deficiency, FPFV = first patient first visit, LPFV = last patient first visit, and LPLV = last patient last visit.

The study population will consist of at least 400 paediatric GHD patients from the GloBE-Reg registry treated with once-weekly somapacitan and fulfilling the eligibility criteria of the present study (see Sections 9.2.2 and 9.2.3). The total duration of the study is planned for 10 years consisting of a 5-year recruitment period in the registry followed by a follow-up period of at least 5 years. Individual patients will be followed up from inclusion into GloBE-Reg until last routine visit within the full study duration, i.e. individual follow-up time is expected to be above 5 years. Patient data are planned to be collected beyond the age of 18 years and irrespective of discontinuation of somapacitan. The main purpose of this study is to observe patients for long-term safety. The planned study duration is from Q4 2024 until Q4 2034.

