9.7.2.1 Analysis of primary endpoint

The primary endpoint is the number of ADRs from baseline to EOS. EOS will differ from patient to patient.

ADRs during the study period will be summarised by MedDRA SOC and PT. This summary is displayed with number and proportion of patients with at least one event, number of events, and event rate (events per 100 patient-years of exposure).

The combined data from NordiNet® IOS and ANSWER will be used as an external comparator for the occurrence of ADRs. The aggregated data from isolated GHD patients from the NordiNET/ANSWER study will be used for comparison of both baseline characteristics and ADR incidence rates. No statistical comparison is planned due to limitations in the observational nature of the data collection.

The correlation between ADR incidence and duration of somapacitan treatment will be analysed with Spearman rank-order correlation.

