9.7.2.2 Analysis of secondary endpoints

Binary secondary endpoints:

The binary secondary endpoints include:

- Incident neoplasm
- Incident T2DM

Incidence rates will be calculated for both endpoints and compared to aggregated data of incident neoplasms from the combined NordiNET/ANSWER study⁶ and incident T2DM from the GeNeSIS study.⁹ From both studies, the incidence rates for isolated GHD will be used for comparison. The SIR with a 95% confidence interval will be used as an additional estimate for neoplasms and new-onset T2DM.

 Protocol
 Date:
 17 July 2024
 Novo Nordisk

 Study ID: NN8640-4787
 Version:
 3.0
 3.0

 UTN: U1111-1294-5941
 Status:
 Final

Page:

25 of 48

Count-data secondary endpoints:

The analyses of the following secondary endpoints (counted from the baseline (week 0) to the EOS^a) will be done in the same way as the analysis of the primary endpoint:

• Number of AEs

EU PAS No.: Pending

- Number of SAEs
- Number of serious ADRs
- Number of medication errors

Continuous secondary endpoints

For the following secondary endpoints (clinical parameters), the change will be estimated by length of follow up and treatment duration.

- Height velocity
- Change in height velocity SDS
- Change in height SDS
- Change in IGF-I SDS
- Change in bone age

Patients reaching near adult height will be evaluated at EOS only for those who are expected to reach near adult height during the study. Change in height SDS in subjects reaching near adult height will be calculated from baseline (week 0) to EOS.

Note: Near adult height can be defined as height velocity <2 cm/year over the last 9 months and chronological age >16 years (males) or >15 years (females) or bone age >16 years (males) and >15 years (females).

IGF-I SDS will be used to evaluate treatment adherence assuming an increase in IGF-I SDS represents a response to GH treatment.

To deal with patients switching medication in-study and on-treatment analyses will be performed as defined below. The analyses will be repeated separately for GH treatment naïve and non-naïve patients previously receiving other GH treatment as data allows.

In-study

The observation period represents the time frame during which patients are considered to be part of the study, regardless of their adherence to somapacitan treatment. The in-study period starts at the time of informed consent and ends at the date of whichever comes first:

- EOS visit (last visit within the study duration)

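### Section 9.5 says 400 patients rule out a doubling of ADR incidence; at a true 2% that result has only a 59% chance, and section 9.7.2.1 plans no statistical comparison to deliver it

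*Protocol*

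**What the plan says.** Section 9.5 bases the sample size on the primary endpoint, using experience from NordiNet IOS, "where 2% of the paediatric patients with GHD experienced an ADR". For sizes from 100 to 500 patients, its Table 9-4 then "shows the 95% confidence interval for an incidence of 2%, derived using the Wilson-score method". The upper limit is given as 4.29% for 300 patients and 3.89% for 400. From this the section concludes that a minimum of 400 "would be required to rule out the doubling of the incidence for ADRs", and it plans for 400. It gives no other reason for that number and no probability of reaching the result.

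Section 9.7.2.1 lists the primary outputs as "number and proportion of patients with at least one event, number of events, and event rate" per 100 patient-years, plus a Spearman correlation with treatment duration. ADR incidence rates are to be set beside aggregated NordiNet/ANSWER data for isolated GHD, but "No statistical comparison is planned due to limitations in the observational nature of the data collection". The only confidence interval named in section 9.7.2 is for other endpoints: "The SIR with a 95% confidence interval will be used as an additional estimate for neoplasms and new-onset T2DM".

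On follow-up, section 9.1 states that "individual follow-up time is expected to be above 5 years", and section 9.1.1 gives a maximum of 10 years. Section 9.5 attaches no follow-up time to the 2%.

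**The concern.** A precision table answers one question: how wide is the interval if a given proportion is observed? Ruling out a doubling raises another: how likely is it that the observed data will put the upper limit below 4%? Section 9.5 answers the first and states its conclusion as if it had answered the second. At an observed 2% the upper limit lies only just under 4%, so ordinary sampling variation in a count expected to be 8 decides the outcome.

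This is the only stated basis for 400 patients in a post-authorisation safety study whose primary endpoint is ADRs. A reader of section 9.5 will expect a safe product to be shown to have less than twice the historical incidence. If 9 patients have an ADR, the final report cannot say so, although the result would fully agree with a true 2%.

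**Working it through.** **Inputs.** All are from section 9.5: assumed proportion 2%; two-sided 95% Wilson interval (z = 1.96); 400 patients; margin 2 × 2% = 4%.

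**1. Reproduce Table 9-4.** With p = x/n, the Wilson limits are

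[p + z²/(2n) ± z·√(p(1−p)/n + z²/(4n²))] / (1 + z²/n)

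For n = 400 and x = 8: z²/(2n) = 0.00480; the root is √(0.0000490 + 0.0000060) = 0.00742; times z this is 0.01454. The limits are (0.02480 ± 0.01454)/1.0096 = 1.02% and 3.90%.

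| n | x at 2% | Recomputed | Table 9-4 |
|---|---|---|---|
| 100 | 2 | 0.55, 7.00 | 0.55, 7.00 |
| 200 | 4 | 0.78, 5.03 | 0.78, 5.02 |
| 300 | 6 | 0.92, 4.29 | 0.92, 4.29 |
| 400 | 8 | 1.02, 3.90 | 1.02, 3.89 |
| 500 | 10 | 1.09, 3.64 | 1.09, 3.64 |

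The two differences are truncation (5.029 and 3.896) and have no consequence.

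**2. Find the cut-off at n = 400.**

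| Patients with an ADR | Wilson upper limit | Below 4%? |
|---|---|---|
| 7 | 3.57% | yes |
| 8 | 3.90% | yes |
| 9 | 4.22% | no |
| 10 | 4.54% | no |

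A doubling is excluded only with 8 or fewer. Clopper-Pearson gives the same cut-off (3.90% at 8, 4.23% at 9).

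**3. Probability of meeting the cut-off at a true 2%.** With X ~ Binomial(400, 0.02), P(X ≤ 8) = 0.593. The chance of not excluding 4% is 1 − 0.593 = 0.407.

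**4. Sensitivity.**

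- At n = 500 the cut-off is 11 and the probability is 0.698.
- At n = 400 and a true proportion of 1.5%, 2.5% or 3%, the probability of excluding 4% is 85%, 33% or 15%.
- At a true 4% it is 2.0%, so the criterion rarely excludes a doubling wrongly. Its weakness is in giving reassurance when there is no excess.
- A one-sided 95% Wilson limit would move the cut-off to 9 (3.83%) and the probability to 72%, but Table 9-4 uses the two-sided interval.

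**5. Compare sections 9.5 and 9.7.2.1.** The first sizes the study to exclude a multiple of a historical incidence. The second, for the same endpoint, disclaims a statistical comparison and names no interval for the proportion on which the sizing rests.

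**6. Time scale.** The proportion of patients with at least one ADR grows with follow-up. Twice the historical 2% is twice the risk only if the two follow-up times are comparable, and the protocol does not give the historical one. The rate per 100 patient-years in section 9.7.2.1 does not have this weakness.

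**The case against.** The strongest defence is that precision-based sizing is normal for a single-arm descriptive safety study. Table 9-4 is correct and labelled as applying to an incidence of 2%, no decision rule turns on 4%, and 400 is a minimum. Most of this stands. Nothing is miscalculated, and a table of interval widths alone would have been unobjectionable. What fails is the added conclusion that a doubling is ruled out. The minimum does not rescue it: section 9.5 plans for 400, and even 500, the largest size tabulated, gives 70%.

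Four stronger readings are tempting, and the protocol does not support them.

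- **That ADRs are not compared with history at all.** Section 9.7.2.1 does plan a descriptive comparison of ADR incidence rates; only a statistical one is excluded.
- **That the interval will never be computed.** The protocol's list does not name it, but section 4.10 defers detail to a statistical analysis plan that is not at hand and could add it. The conflict between sections 9.5 and 9.7.2.1 exists either way.
- **That longer follow-up than the comparator's pushes the probability well below 59%.** That holds only if the margin stays at 4% while the expected proportion rises. If the margin is scaled to the same follow-up, the direction reverses, because more events are expected. Neither study's mean follow-up is given.
- **That the 2% comes from a different cohort than the benchmark.** Section 9.5 names NordiNet IOS but cites the joint NordiNet IOS and ANSWER publication, so the cohort behind the figure cannot be settled from the protocol.

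**Conclusion.** The concern holds as a fault of inference and consistency, not of arithmetic. With 400 patients, a two-sided 95% Wilson interval and a true proportion of 2%, the upper limit falls below 4% with probability 59%, and fails to do so with probability 41%. The stated property is therefore not assured, and section 9.7.2.1 as written does not set out to evaluate it.

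The 59% is exact under those inputs. It depends on 2% being the right cumulative proportion for this study's follow-up, which the protocol does not establish. The finding does not show that 400 patients are too few for a descriptive study; it shows that the reason given for 400 promises more than the design delivers.

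**What to change.** Keep 400 patients and change the wording in two places.

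- **Section 9.5.** Replace the unqualified statement on ruling out a doubling with text such as: *If 2% is observed, the 95% Wilson interval is 1.02% to 3.90%. If the true proportion is 2%, 400 patients give a 59% probability that the upper limit is below 4% (at most 8 patients with an ADR).*
- **Section 9.7.2.1.** Report the 95% Wilson interval for the proportion of patients with an ADR, and a 95% interval for the already planned rate per 100 patient-years. State that any remark on doubling relative to NordiNet/ANSWER will be made on the patient-year scale and descriptively. This agrees with the existing decision not to make a statistical comparison.

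The cost is a less favourable stated assurance and one extra table column. No patients or data items are added.

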4.9 Study sample size

The study is planned for the sample size of at least 400 patients (inclusive of both naïve and non-naïve).

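### Section 9.5 overstates what 400 patients deliver: under its own 2% assumption, the upper 95% limit falls below a doubled ADR incidence only about 59% of the time

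*Protocol*

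**What the plan says.** Protocol section 9.5 sizes the study on the proportion of patients with at least one ADR. It takes the planning value from the NordiNet IOS experience, "where 2% of the paediatric patients with GHD experienced an ADR". Table 9-4 then "shows the 95% confidence interval for an incidence of 2%, derived using the Wilson-score method", for 100 to 500 patients. The row for 400 reads 1.02% to 3.89%; the row for 300 has an upper limit of 4.29%.

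From this the section concludes that "a sample size of at least 400 patients" "would be required to rule out the doubling of the incidence for ADRs", and closes: "Therefore, the study is planned for the sample size of 400 patients". It states no power and no probability that the upper limit will fall below any value.

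Section 9.7.2.1 describes the primary analysis as numbers and proportions of patients, event counts and rates per 100 patient-years. The external data are set alongside these: "No statistical comparison is planned due to limitations in the observational nature of the data collection".

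**The concern.** An interval calculated at the expected proportion shows the precision obtained if the data land exactly on that proportion. It does not show how often the data will be at least that favourable. Section 9.5 moves from the first to the second: because the interval at 2% stops short of 4%, it says this size is what ruling out a doubling requires.

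At 400 patients the expected count under the assumption is 400 × 0.02 = 8, and the tabulated upper limit lies only about 0.1 percentage points below 4%. Little more than half of the possible outcomes can then be expected to meet the stated property.

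This sentence is the protocol's only justification of the study size, so a reader of the final report is likely to hold the result against the 4% benchmark. If somapacitan has exactly the assumed incidence, the interval will still include 4% in about 4 of 10 such studies. Without that figure stated in advance, an unremarkable result could be taken for a safety signal.

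**Working it through.** **Inputs, all from section 9.5.** Assumed proportion p = 2%. Interval: two-sided 95% Wilson score, z = 1.96 (z² = 3.8415). Value to be excluded: 2 × 2% = 4%. Size: n = 400.

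**Step 1. Reproduce Table 9-4.** With x patients having an ADR and p̂ = x/n, the Wilson limits are

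[p̂ + z²/(2n) ± z·√(p̂(1 − p̂)/n + z²/(4n²))] / (1 + z²/n).

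At n = 400 and x = 8:
- p̂ + z²/(2n) = 0.02 + 0.004802 = 0.024802
- z·√(0.000049 + 0.000006002) = 1.96 × 0.007416 = 0.014536
- divisor = 1.009604
- limits = 0.010266/1.009604 = 1.02% and 0.039338/1.009604 = 3.90%

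The other rows reproduce in the same way: (0.55, 7.00), (0.78, 5.03), (0.92, 4.29) and (1.09, 3.64). The printed 5.02 and 3.89 appear truncated rather than rounded (5.029 and 3.896), which is immaterial.

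**Step 2. Find the largest count that excludes 4% at n = 400.** At x = 9, p̂ = 2.25%:
- upper limit = (0.027302 + 0.015306)/1.009604 = 4.22%

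The upper limits for 7, 8, 9 and 10 patients are 3.57%, 3.90%, 4.22% and 4.54%. So 4% is excluded only with 8 or fewer patients.

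**Step 3. Find how often that happens.** With X binomial (400, 0.02), P(X ≤ 8) = 0.593, so a doubling is not excluded with probability 0.407. At other true proportions P(X ≤ 8) is 0.85 at 1.5%, 0.33 at 2.5% and 0.15 at 3.0%. At a true 4% it is 0.020, so the interval rarely excludes a doubling that is real.

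**Step 4. Repeat for every row of Table 9-4, at a true 2%.**

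| n | Upper limit if 2% is observed | Largest count with upper limit below 4% | Probability of that count or fewer |
|---|---|---|---|
| 100 | 7.00% | 0 | 13% |
| 200 | 5.03% | 2 | 24% |
| 300 | 4.29% | 5 | 44% |
| 400 | 3.90% | 8 | 59% |
| 500 | 3.64% | 11 | 70% |

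**Step 5. Check other interval methods at n = 400.** Clopper-Pearson gives 59%, continuity-corrected Wilson 45%, and Wald or one-sided 95% limits 72%. The result does not depend on the choice of Wilson.

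**The case against.** The best defence is that section 9.5 is precision-based sizing. It presents the interval for a 2% incidence, ties its conclusion to that table, and promises no power. On the premise that exactly 2% is observed, the upper limit is indeed below 4%. Choosing a size this way is legitimate, and the table stands. What does not follow is the closing sentence: saying that a size is required to rule out a doubling describes what the study can do, and the table cannot show that without the probability of a result at least this favourable. Even on the fixed-2% reading, 400 is only the first tabulated size below 4%; the formula crosses 4% at n = 369.

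A second defence is that nothing in the analysis turns on 4%. This also stands. Section 9.7.2.1 plans no statistical comparison of ADRs with the external data, so the 41% is not the failure rate of any planned test. Section 9.9 further commits the final report to discussing comparability with the external studies.

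A third is that 400 is a minimum. More patients would help (70% at 500, 77% at 600), but section 9.5 attaches its claim to 400.

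A reader might infer from all this that the study is too small. An 80% probability is first reached at 582 patients and held at every size from 644. But the protocol sets no such target, so these figures show no shortfall against anything it adopted. A reader might also infer that a regulatory commitment would go unmet. Section 7 describes the requirement as conducting the registry study to investigate long-term safety and clinical parameters; it does not tie the requirement to excluding a doubling.

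**Conclusion.** The point holds as an overstated sample-size justification, of moderate severity. Under section 9.5's own planning value and interval method, 400 patients bring the upper limit below 4% with probability 59%, and one ADR patient above the expected 8 is enough to lose the property.

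It would be wrong to call this an arithmetic error or a miscalculated power: Table 9-4 reproduces and no power was stated. The fault lies in the conclusion drawn from the table. It is confined to section 9.5; section 4.9 repeats the number of patients without the claim.

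The 59% assumes independent patients with a common 2% probability of at least one ADR over their follow-up, exactly 400 patients, and a doubling measured against a fixed 2%. Varying follow-up or uncertainty in the comparator figure would change the number, but would not make the table support the sentence.

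**What to change.** In section 9.5, replace the sentence about ruling out a doubling with a precision statement, for example: *If the observed proportion is 2%, the 95% confidence interval with 400 patients is 1.0% to 3.9%. If the true proportion is 2%, the probability that the upper limit is below 4% is about 59%.*

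Alternatively, keep the reference to a doubling and add a column to Table 9-4 giving that probability for each row: 13%, 24%, 44%, 59% and 70%.

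The cost is one sentence or one column. The planned number of patients, the endpoints, the data collection and the analyses stay as they are. The stated property becomes less favourable, but it becomes one that the table supports.

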9.6 Data management

All data for this study will be drawn from GloBE-Reg (see Section 9.4). GloBE-Reg is responsible for the collection of the data from paediatric patients with GHD treated with somapacitan (see Section 9.3). Data are collected by the collaborating centres during visits as part of the routine clinical practice and are subsequently included in GloBE-Reg. An overview of the data can be found in the GloBE-Reg website. 17,18

The variables included in this study are listed in Section 9.3.

Extracts from GloBE-Reg will be submitted electronically to Novo Nordisk A/S for inclusion in the interim and final study reports.

Analysis of all study data is the responsibility of Novo Nordisk A/S.

Protocol		Date:	17 July 2024	Novo Nordisk
Study ID: NN8640-4787	CONFIDENTIAL	Version:	3.0	
UTN: U1111-1294-5941	CONFIDENTIAL	Status:	Final	
EU PAS No.: Pending		Page:	24 of 48	

Appropriate measures such as encryption or deletion must be enforced to protect the identity of patients when transmitting data, in all presentations and publications as required by local/regional/national requirements.

